4.4. Claims and Intended Performance

The proposed intended use statement for DreamKit is as follows, with the parts relevant to this study bolded (wording may change before regulatory submission):

*The DreamKit device is a physiologic data recorder intended to collect and record data for use by clinical software used in polysomnography and sleep disorder studies **for the diagnosis of sleep related breathing disorders**. The Plethysmography-Acquired Respiratory Effort (PARE) algorithm provides a respiratory effort signal acquired from the DreamKit photoplethysmography signal that correlates with traditional respiratory effort signals used in polysomnography. The DreamKit with PARE provides the information required to **detect apneas and hypopneas and classify these***

Document ID:	SRC_SLE_Sparkle_PSG_2020_10908	Document title:		Classification:	Confidential
Modified:	26 July 2021	Clinical Investigation Protocol ICH E6 Aligned			
Version:	5	User Tool ID:	16.2.6UserTool0004		
Status:	Final	User Tool Version Date	5June2019	Page:	17

respiratory events as central, mixed, or obstructive. It is intended for adult use and can be used in a hospital, clinic, or patient home.

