6.5. Strategies for Recruitment and Retention

Participants will be recruited such that the overall sample will comprise approximately 50% OSA, 30% central sleep apnea (CSA; with or without Cheyne-Stokes respiration), and 20% healthy (no SDB). Recruitment for the OSA and CSA participants will proceed by targeting those with a known diagnosis and/or those currently using therapy for SDB and/or those considered by the site investigator to be high-risk. The sites may choose to administer the STOP-BANG questionnaire⁹ during phone screening for risk stratification, but this is optional. Due to night-to-night SDB severity variability as well as the natural history of SDB, the diagnosis of each participant may not be known ahead of time and as such, our inclusion/exclusion criteria do not reference OSA or CSA diagnostic criteria.

The PSGs will be scored throughout the study, and each participant will be assigned to a diagnostic category (see Section 8.1.6). This information will be used to guide further recruitment to ensure the proportions of OSA, CSA, and no SDB referenced above, as well as to ensure a wide range of SDB severity. The diagnostic category assigned in this study will be based solely on PSG scoring output without any other clinical information, and will have no bearing on clinical care.

It is anticipated that racial/ethnic minorities will represent at least 20% of the sample, and that males and females will comprise at least 30% of the sample each. These parameters are approximate expectations only.

Document ID:	SRC_SLE_Sparkle_PSG_2020_10908	Document title:		Classification:	Confidential
Modified:	26 July 2021	Clinical Investigation Protocol ICH E6 Aligned			
Version:	5	User Tool ID:	16.2.6UserTool0004		
Status:	Final	User Tool Version Date	5June2019	Page:	22

Clinical Investigation Protocol ICH E6 Aligned

All participants will be enrolled within the US. Recruitment will be the responsibility of the site, and will take place through advertisements, the pipeline at local clinic/s, and/or by inspection of local medical records. As this study has only two visits, it is not likely that participants will drop-out or be lost to follow-up before study completion and therefore no specific strategies for retention are required.

Document ID:	SRC_SLE_Sparkle_P SG_2020_10908	Document title:		Classification:	Confidential
Modified:	26 July 2021	Clinical Investigation Protocol ICH E6 Aligned			
Version:	5	User Tool ID:	16.2.6UserTool0004		

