8.1.6. Signal quality and other feedback to sites

Data processing and scoring will take place throughout the study, allowing continual feedback from Philips to the sites.

The AASM clinical practice guidelines state that a diagnosis can be made using a HSAT only if the recording includes at least four hours of technically adequate oximetry and flow data;¹⁵ studies that do not meet these criteria will not be included in the evaluable dataset. Collection of persistent invalid PSGs or other quality issues may prompt Philips to request the site to undergo troubleshooting or re-training. Note that if a PSG is excluded from the evaluable dataset for technical reasons but the investigator considers the participant to be suitable for a repeat test, a repeat overnight visit can be scheduled.

Each PSG will be categorized as follows (note that these categories are not mutually exclusive; as such, groups will be filled in the order listed below):

- PSG-CAI ≥30 events/hour (~10% of sample);

Document ID:	SRC_SLE_Sparkle_PSG_2020_10908	Document title:		Classification:	Confidential
Modified:	26 July 2021	Clinical Investigation Protocol ICH E6 Aligned			
Version:	5	User Tool ID:	16.2.6UserTool0004		
Status:	Final	User Tool Version Date	5June2019	Page:	28

- PSG-OAI ≥30 events/hour (~17% of sample);
- PSG-CAI 15-29.9 events/hour (~10% of sample);
- PSG-OAI 15-29.9 events/hour (~17% of sample);
- PSG-CAI 5-14.9 events/hour (~10% of sample);
- PSG-OAI 5-14.9 events/hour (~17% of sample);
- PSG-AHI <5 events/hour (~20% of sample).

The proportion of participants falling into these categories across all sites will be conveyed to sites periodically, along with guidance to optimize recruitment according to the approximate goals listed in Section 6.5. Note that the category assigned during this process may differ from a clinical diagnosis; this process will take place only to ensure that recruitment proceeds according to the description in Section 6.5.

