12.1.8. Exploratory Analyses

Analyses of indices

- We will calculate the ICC for absolute agreement (two-way, mixed effect) between the PSG and DreamKit ODI3%, total respiratory events, total apneas, total hypopneas, total obstructive apneas, total central apneas, and total mixed apneas, along with 95% CIs.
- We will construct a confusion matrix and calculate Cohen's kappa (linear weighted) for four categories of disease severity determined by the PSG and DreamKit (AHI 0-4.9, 5-14.9, 15-29.9, and ≥ 30 events/hour).
- We will construct a confusion matrix depicting true-positives, false-positives, true-negatives, and false-negatives for the AHI, CAI, and ODI3% (separately) at thresholds of 5, 15, 20, 30, and 40 events/hour.
- We will calculate the accuracy (percentage agreement between PSG and DreamKit), sensitivity, specificity, positive predictive value, negative predictive value, positive likelihood ratio, and negative likelihood ratio for each threshold of the above indices.
- We will construct a receiver operating characteristic curve and calculate the area under the curve for each threshold of the above indices.
- We will construct a Bland-Altman plot for each threshold of the above indices, including a 95% CI for the upper and lower limits of agreement.

Document ID:	SRC_SLE_Sparkle_PSG_2020_10908	Document title:		Classification:	Confidential
Modified:	26 July 2021	Clinical Investigation Protocol ICH E6 Aligned			
Version:	5	User Tool ID:	16.2.6UserTool0004		
Status:	Final	User Tool Version Date	5June2019	Page:	38

- We will construct a scatter plot with regression line for each threshold of the above indices.
- We will repeat all analyses listed above using the AASM alternative hypopnea criteria.

Event-level analyses

- We will construct a 2x2 confusion matrix based on the presence/absence of events by adapting the methodology described in the AASM Inter-Scorer Reliability Program: Respiratory Events (2014).¹⁶ Each epoch staged as sleep per the PSG will be deemed ‘positive’ if it contains at least one respiratory event of any type, and ‘negative’ if it contains no respiratory events/s.

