- We will construct a 4x4 confusion matrix based on apnea differentiation (obstructive apnea, central apnea, mixed apnea, no event), following the above methodology using events staged as sleep per the PSG, and calculate Cohen’s kappa.¹⁷ In cases where a single epoch contains more than one event, the first event will be used for categorization. Mixed events will be categorized independently if we observe at least five mixed events/hour in at least 5% of participants and at least ten mixed events/hour in at least 2% of participants in the evaluable dataset; otherwise, mixed events will be placed in the obstructive category to create a 3x3 confusion matrix.

Signal quality analyses

- Finally, we will compare the average percentage of useable signal quality from the DreamKit respiratory effort signal (PARE algorithm) and PSG (thoracic and/or abdominal belts).

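### The planned kappa for apnea differentiation mixes event detection and participants' dominant apnea type with event-level typing, so it cannot show event-level typing by itself.

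*Combined protocol and SAP*

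**What the plan says.** The event-level part of section 12.1.8 states: "We will construct a 4x4 confusion matrix based on apnea differentiation (obstructive apnea, central apnea, mixed apnea, no event". The matrix is built "following the above methodology using events staged as sleep per the PSG, and calculate" Cohen's kappa. The methodology referred to is the bullet before it, where the unit is the epoch: "Each epoch staged as sleep per the PSG will be deemed" positive or negative. If an epoch holds more than one event, the first one counts. If mixed apneas are rare they join the obstructive class, and the matrix becomes 3x3.

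The section specifies no kappa per participant or stratified by participant, no version limited to epochs that both systems score as an apnea, and no confidence interval for this kappa. It does not use the word pooled. A single matrix built from epochs is most naturally read that way.

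Three other places bear on it. Section 4.3 names event-level differentiation as an aim. The intended use in 4.4 covers classifying "respiratory events as central, mixed, or obstructive". Section 6.5 recruits "approximately 50% OSA, 30% central sleep apnea", with the remaining 20% free of sleep-disordered breathing. Section 8.1.6 fills severity bands such as "PSG-CAI ≥30 events/hour (~10% of sample" and "PSG-OAI ≥30 events/hour (~17% of sample", with two lower bands of the same sizes for each type.

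**The concern.** A kappa offered as evidence of apnea differentiation should be low for a device that cannot tell one apnea type from another. Two features of this one work against that.

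- **The no-event class.** Most sleep epochs contain no apnea, and agreeing on which ones do is detection, not typing. That agreement enters the same kappa.
- **The recruited contrast.** Chance agreement is computed from the overall margins. If some participants are mainly central and others mainly obstructive, knowing which kind of participant is being recorded beats that chance level even when nothing is known about the individual event.

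This matrix is the only planned analysis that compares apnea type event by event. The 2x2 event matrix ignores type. The ICCs for CAI and for total obstructive, central and mixed apneas, and the CAI thresholds, compare participant-level indices or counts. If the kappa cannot separate typing from the other two sources, the trial does not directly answer its own question about event typing.

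**Working it through.** **The plan's own figure.** The protocol gives no expected value, target or precision for this kappa, so there is none to reproduce.

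**Inputs from the documents.** n = 200. From 8.1.6, three central bands of about 10% (20 participants each) and three obstructive bands of about 17% (34 each). The remainder is 200 − 60 − 102 = 38.

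**Assumptions, not in the documents.** Six hours of sleep in 30-second epochs (720 per participant). Apneas per hour of 40, 22 and 10 in the central bands, 45, 22 and 10 in the obstructive bands, and none in the other 38. One apnea per epoch and no mixed apneas. 85% of apneas detected, with 2% false-positive epochs. The central share of apneas is 95/85/75/65% in central participants, paired with 3/5/10/15% in obstructive participants.

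**Counts.** Central participants: 20 × (40+22+10) × 6 = 8,640 apneas. Obstructive participants: 34 × (45+22+10) × 6 = 15,708. Total 24,348. Epochs: 200 × 720 = 144,000, of which 119,652 have no apnea. Detected apneas: 0.85 × 24,348 = 20,695.8. Agreed no-event epochs: 0.98 × 119,652 = 117,259.

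**Formula.** κ = (po − pe)/(1 − pe), with pe from the overall margins.

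**Worked case, shares 85% and 5%.** Central apneas: 0.85 × 8,640 + 0.05 × 15,708 = 8,129.4, or 33.4% of apneas. PSG margins (central, obstructive, none): 0.0565, 0.1126, 0.8309. The device's no-event margin is (0.15 × 24,348 + 117,259)/144,000 = 0.8397.

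- *Random typing at the overall mix.* Type agreement is 0.334² + 0.666² = 0.555. po = (0.555 × 20,695.8 + 117,259)/144,000 = 0.894; pe = 0.713; κ = 0.181/0.287 = 0.63.
- *Majority-type rule* (every apnea gets the participant's dominant type; the 38 default to obstructive). Type agreement is (7,344 + 14,922.6)/24,348 = 0.915. po = (0.915 × 20,695.8 + 117,259)/144,000 = 0.946; pe = 0.713; κ = 0.233/0.287 = 0.81. Within each participant the label is constant, so po = pe and the type kappa is 0.
- *Perfect typing* (false positives follow each participant's own mix, half and half in the 38). po = (20,695.8 + 117,259)/144,000 = 0.958; pe = 0.713; κ = 0.245/0.287 = 0.85.

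**All four mixes, kappa with the no-event class:**

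| Central share (central / obstructive participants) | Random typing | Majority-type rule | Perfect typing |
|---|---|---|---|
| 95% / 3% | 0.63 | 0.84 | 0.85 |
| 85% / 5% | 0.63 | 0.81 | 0.85 |
| 75% / 10% | 0.63 | 0.78 | 0.85 |
| 65% / 15% | 0.63 | 0.74 | 0.85 |

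With perfect detection, random typing scores 0.74 to 0.75.

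**Removing the no-event class.** Over jointly detected apneas the random device falls to 0, as it should. The majority-type rule still scores 0.92, 0.81, 0.66 and 0.51 if participants are pooled. Both steps are therefore needed: restriction to jointly scored apneas, and chance agreement computed within participant.

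**Behaviour of a stratified kappa.** Take Σ nᵢ(poᵢ − peᵢ)/Σ nᵢ(1 − peᵢ) for a device that types each apnea correctly 92% of the time. In the first mix a central participant has pe = 0.840 and an obstructive one 0.871. The result is (8,640 × 0.080 + 15,708 × 0.049)/(8,640 × 0.160 + 15,708 × 0.129) = 0.43. Across the four mixes it is 0.43, 0.61, 0.72 and 0.77, although typing accuracy is constant.

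**Sensitivity to the type share.** A second set of assumptions uses the same dominant-type share in both groups, apnea indices of 40, 22 and 10, and 1 per hour in the 38. At shares of 0.60, 0.70, 0.80, 0.90 and 0.95 the majority-type rule scores 0.66, 0.70, 0.75, 0.80 and 0.83 with the no-event class, against 0.61 to 0.62 for random typing. Its type-only pooled kappa is 0.19, 0.38, 0.58, 0.78 and 0.88. Per-participant kappas that keep the no-event class do not help: with perfect detection their mean for this rule is still 0.76 to 0.93.

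**The case against.** The strongest reply is that the analysis is exploratory, has no threshold, and produces the full matrix, so a reader can see type errors among jointly detected apneas. That is true of pooled errors. The matrix cannot show within-participant typing, because it discards participant identity.

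Second, the majority-type rule is artificial. Section 8.1.5 classifies each apnea from respiratory effort during that event. Where the rule scores highest it also types about 96% of apneas correctly. This stands: nobody suggests that DreamKit works this way. The rule only shows what the kappa cannot rule out.

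Third, the CAI and apnea-count ICCs would catch gross mistyping. At a 65% central share, calling everything central inflates central counts by 1/0.65, about half. At a 95% share the inflation is only 1/0.95, about 5%. The ICCs help where participants are mixed and do little where the kappa is most misleading.

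Fourth, section 8.1.6 says its categories overlap, so participants may be less contrasted than assumed. This stands and reduces the second source. It does not touch the first.

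Finally, a stratified kappa has its own distortion, since it moves from 0.43 to 0.77 at constant accuracy. This argues against using it as a sole replacement, not against reporting it beside the planned kappa.

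**Conclusion.** The concern holds in a limited form. As the plan reads, the kappa does not isolate event-level typing. Under the stated assumptions about 0.63 of it is reached with random typing, and about 0.74 to 0.84 with no within-person discrimination, against about 0.85 for perfect typing. The figures rest on assumed apnea rates, detection and within-participant type shares, and on reading the single matrix as pooled.

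A reader might go further in four ways that the documents do not support.

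- Patient-level differences are not the whole explanation. The no-event class contributes much of the value.
- The values 0.92 to 0.51 belong to a two-class kappa that the plan does not compute.
- The plan does not treat epochs as independent, because it specifies no interval or test for this kappa.
- Hypotheses 1 and 2 are not affected. They rest on ICCs of AHI and CAI.

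What remains at stake is the direct evidence for the classification wording in 4.4. The change is worth making before analysis.

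**What to change.** In 12.1.8, state whether the matrix pools all participants' epochs. Keep it and its kappa, and add:

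- (a) type agreement and kappa restricted to epochs that both systems score as an apnea;
- (b) a participant-stratified version of that kappa, with a note that its value depends on case mix;
- (c) the share of each participant's minority-type apneas, such as central apneas in a mainly obstructive participant, that DreamKit types as PSG does;
- (d) 95% confidence intervals from resampling participants.

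Statements about apnea differentiation should cite these together, not the pooled kappa alone.

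The cost is a few sentences in the plan and a few lines of code, with no new data. The added estimates will be lower and less precise, and participants with almost only one apnea type will contribute little to (b) and (c).

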8.1.5. Data processing and scoring

All data processing will take place at Philips using Sleepware software. The analyst will import the DreamKit and PSG signals, ensuring that the signals are mapped correctly. The analyst will then inspect the time alignment of the DreamKit and PSG signals; if necessary, the DreamKit time may be adjusted to ensure synchronization with the PSG pulse rate and/or flow signal/s recorded from the shared nasal cannula.

Automated scoring using Somnolyzer will be used for PSG and DreamKit respiratory event detection within the rest period (time between lights off and lights on). Sleep staging during the rest period will be undertaken using Somnolyzer (PSG) or CReSS (DreamKit) algorithms. Sleep staging and event scoring will follow AASM guidelines.¹⁴ Apneas will be scored when there is a ≥90% reduction in airflow for at least ten seconds (Section IX Part 1, G1), and classified as obstructive (continued or increased respiratory effort throughout), central (absence of respiratory effort throughout), or mixed (initial absence followed by resumption of respiratory effort). For our primary and secondary analyses, hypopneas will be scored according to the AASM recommended criteria; that is, a ≥30% reduction in airflow for at least ten seconds, associated with a SpO₂ desaturation of ≥3% (Section IX Part 1, H1A). We will perform a sensitivity analysis in which hypopneas are scored according to the alternative criteria (a ≥30% reduction in airflow for at least ten seconds, associated with a SpO₂ desaturation of ≥4%; Section IX Part 1, H1B).

The following metrics will be calculated for both the PSG and DreamKit:

- AHI: Number of apneas and hypopneas divided by TST;
- CAI: Number of central apneas divided by TST;
- ODI: Number of SpO₂ desaturations (≥3%) divided by TST.

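### Unless the mixed-apnea rate condition in Section 12.1.8 is met, the plan gives no event-level result on telling mixed from obstructive apneas, a distinction the intended use claims

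*Combined protocol and SAP*

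**What the plan says.** Section 8.1.5 scores three apnea types, with mixed as its own type: "mixed (initial absence followed by resumption of respiratory effort". Section 4.4 gives an intended use in which the device lets apneas and hypopneas be detected and classifies "respiratory events as central, mixed, or obstructive". That section says the parts relevant to this study are in bold, and the bold runs into the classification clause.

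The analysis of event type is in Section 12.1.8, among the exploratory analyses. It is a "4x4 confusion matrix based on apnea differentiation (obstructive apnea, central apnea, mixed apnea, no event") built on epochs that the PSG stages as sleep, with Cohen's kappa. No performance target is set for that kappa. Mixed remains a separate class only with "at least five mixed events/hour in at least 5% of participants and at least ten mixed events/hour in at least 2% of participants" of the evaluable dataset. If either part fails, "otherwise, mixed events will be placed in the obstructive category to create a 3x3 confusion matrix".

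The section does not say that the four-class matrix or its kappa is also reported after merging. Nor does it say whether the mixed rate is counted on the PSG or on the DreamKit recording.

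Two other analyses in Section 12.1.8 involve mixed events whatever the rule decides: an ICC for "total obstructive apneas, total central apneas, and total mixed apneas, along with 95% CIs", and a 2x2 epoch matrix for the presence of a respiratory event of any type.

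**The concern.** The matrix is the only planned analysis that asks, event by event, whether the device gives an apnea the same type as the PSG does. If the condition fails, mixed and obstructive become one category on both axes. An epoch that the PSG scores as mixed and the device scores as obstructive, or the reverse, then sits on the diagonal as agreement.

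Two things follow. The reader cannot see how well mixed is separated from obstructive, although the claim names both. And the reported kappa answers an easier question than the four-class kappa would have.

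Nothing in the design secures enough mixed apneas to avoid this. The recruitment categories in Section 8.1.6 are defined by PSG-CAI, PSG-OAI and PSG-AHI; none is defined by mixed apneas.

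**Working it through.** **No planned figure to reproduce.** The documents state no expected kappa and no expected mixed-apnea rate. The inputs from the documents are the two rate conditions (Section 12.1.8) and the target of 200 evaluable participants (Section 12.1.1).

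**The rule in counts.** 0.05 × 200 = 10 participants with at least 5 mixed events/hour, and 0.02 × 200 = 4 participants with at least 10/hour. Both are needed. If the true share of participants with at least 5/hour were 4%, 5% or 6%, the binomial probability of seeing 10 or more in 200 is 0.28, 0.55 or 0.77. This covers the first condition only; requiring the second as well cannot raise it. Those shares are assumptions, so whether merging will occur cannot be predicted from the documents.

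**Effect on kappa.** Kappa = (Po - Pe)/(1 - Pe), where Po is observed and Pe is chance agreement. Merging mixed (M) into obstructive (O) has two effects:

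- Po rises by the two cells M-called-O and O-called-M.
- Pe rises by r(O)·c(M) + r(M)·c(O), where r is the PSG share and c is the device share.

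Kappa therefore rises exactly when the gain in Po exceeds (1 - four-class kappa) times the gain in Pe.

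**Assumed inputs (none from the documents).** PSG epochs: 8% obstructive, 5% central, 0.5% to 3% mixed, the rest no event. Device calls as O/C/M/none:

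- obstructive epochs: 75/5/3/17%
- central epochs: 8/70/3/19%
- no-event epochs: 1.5/1/0.3/97.2%
- mixed epochs: varied by scenario

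**One case in full.** 2% mixed epochs, called O/C/M/none 60/10/10/20%.

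- Device shares: O 0.08875, C 0.04950, M 0.00845, none 0.85330.
- Four-class: Po = 0.0600 + 0.0350 + 0.0020 + 0.8262 = 0.9232. Pe = 0.08×0.08875 + 0.05×0.04950 + 0.02×0.00845 + 0.85×0.85330 = 0.73505. Kappa = 0.18815/0.26495 = 0.710.
- Merged: Po = 0.9232 + 0.0120 + 0.0024 = 0.9376. Pe = 0.73505 + 0.08×0.00845 + 0.02×0.08875 = 0.73750. Kappa = 0.20010/0.26250 = 0.762.

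**Other cases, same method.**

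| Mixed share of epochs | How PSG-mixed epochs are called | Four-class kappa | Merged kappa | Change |
|---|---|---|---|---|
| 2% | mostly obstructive (10% correct) | 0.710 | 0.762 | +0.052 |
| 3% | none called mixed, mostly obstructive | 0.683 | 0.764 | +0.081 |
| 2% | mostly central (10% correct) | 0.710 | 0.725 | +0.014 |
| 2% | 75% correct | 0.760 | 0.768 | +0.008 |

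Over 20 such scenarios the change ran from +0.008 to +0.081. Two extreme tables at 3% mixed, with the false mixed calls altered, gave small falls: 0.787 to 0.784 when mixed was almost perfectly classified, and 0.701 to 0.700 when confusion was almost only between mixed and central.

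**What merging hides.** Compare the first and last rows. Mixed-class sensitivity is 10% in one and 75% in the other. The four-class kappas differ (0.710 and 0.760); the merged kappas barely do (0.762 and 0.768).

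**The case against.** The case for leaving the plan alone has real strength. The rule is fixed in advance with numeric cut-offs, so nobody chooses the matrix after seeing the result. Merging a sparse class is ordinary practice. The analysis is exploratory, has no kappa target and bears on neither hypothesis. A kappa from an openly merged 3x3 matrix correctly describes the discrimination it tests; it would mislead only if read as a four-class result, and the plan does not say it would be presented that way. Section 4.4 also notes that the intended-use wording may change before submission. All of this stands, and it limits the point to a small improvement in reporting.

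Two stronger readings might be inferred, and the documents support neither.

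- *That merging leaves no event-level evidence on mixed apneas.* In the 3x3 matrix, mixed events are still tested against central and against no event, and they count as positives in the 2x2 matrix. Only the mixed-versus-obstructive split is lost.
- *That merging necessarily or greatly inflates kappa.* The rise is usual but not certain, and it can be close to zero.

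The ICC of total mixed apneas is also genuine evidence on the class. It does not fill the gap, because missed and false mixed calls within a participant can offset each other and still give matching totals.

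**Conclusion.** The concern holds in a limited form. If either rate condition fails, the plan as written yields no event-level result on separating mixed from obstructive apneas, although the intended use names both. Pre-specification rules out a choice made after seeing the data; it does not supply the missing result.

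The effect on kappa is about -0.003 to +0.08, largest when mixed apneas are mistaken for obstructive ones. That range rests wholly on assumed epoch shares and error rates, with the no-event class included as Section 12.1.8 plans. How likely merging is cannot be judged from the documents. No primary or secondary conclusion changes. This is worth fixing because it is cheap, not because it threatens the study.

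**What to change.** In Section 12.1.8, state that the unmerged 4x4 matrix will always be reported, with its kappa and with the sensitivity and positive predictive value of the mixed class. When the merging condition applies, give the 3x3 matrix and its kappa as an additional result, labelled as combining mixed with obstructive. The same sentence could name the recording (PSG or DreamKit) on which the mixed rate is counted.

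The events are already scored by type, so the cost is a few words and one extra table. The drawback is that the mixed row will be imprecise when mixed events are rare; showing the counts makes that plain.
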